AEs will be presented in listings, and TEAEs will be summarized. Individual results of laboratory tests (hematology, chemistry, and urinalysis) will be recorded at baseline and post-dose, and changes from baseline will be summarized using shift tables. Individual vital signs will be recorded and observed values and changes from baseline will be summarized. Individual results of quantitative ECG parameters from the 12-lead safety ECGs will be listed and observed values and changes from baseline will be summarized. All summaries will be performed by placebo, each CVN766 dose level (fasted and fed separately), and CVN766 single-dose overall, and separately CVN766 multiple-dose cohorts overall. Placebo data will be pooled across single-dose cohorts and separately pooled across multiple-dose cohorts. Physical exam findings will be presented in data listings.

PK Measures:

Concentrations of CVN766 in plasma and CSF will be summarized by dose over each scheduled sampling time using descriptive statistics. Individual plasma and CSF concentration data versus time will be presented in a data listing. Individual and mean plasma and CSF concentration data will be presented graphically.

PK parameters of CVN766 will be summarized by dose using descriptive statistics. Dose proportionality will be assessed graphically and using a power model.

The concentrations of CVN766 in plasma and CSF will be compared.

Sample Size Justification:

The sample size chosen of 8 subjects per cohort (6 active: 2 placebo) is considered sufficient for evaluating the safety, tolerability, and PK of each cohort. The sample size was not based on statistical power considerations.

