
will be repeated in a single cohort (S3) after ingestion of a standardized high-fat, high-calorie meal according to FDA Guidance for Industry (Food-effect bioavailability and fed bioequivalence studies, Dec 2002). Once the safety of the S3 cohort dose level has been assessed, the S3 cohort subjects will return to the clinic (no sooner than 14 days after their prior dose, or at least 4 half-lives, has lapsed based on preliminary PK data, whichever is longer). They will receive the same dose as before, administered after ingesting a standardized breakfast. Subjects will finish the entire content of their breakfast within 25 minutes and will receive an investigational product 30 minutes (\pm 5 minutes) after beginning the meal. Sentinel dosing will not be required for subjects returning to the clinic for the fed regimen. If the CVN766 PK parameters in the fasted S3 cohort reveal poor absorption with inconclusive results, the fed cohort will be deferred until a higher dose level.

Subjects for all cohorts will be admitted to the study unit 1 day prior to dosing and remain in the unit for safety and PK assessments. On Day 1, subjects will undergo safety monitoring and PK sampling from blood plasma through 72 hours post-dose and, for cohort S3 (fasted) only, from CSF via lumbar puncture at 3 hours post-dose. The total confinement period will be 4 nights, unless extended at the discretion of the Investigator, e.g., for monitoring and/or management of AEs. Follow-up assessments will occur on approximately Days 8 and 14 and +21 and +28 for cohort S3.

A summary of the single-dose regimen visit schedule is presented below:

Screening ^a	Inpatient Check-in	Dosing, PK, CSF & Safety Assessments ^b	Inpatient PK, Safety and Lumbar Puncture Site Assessments (S3 fasted)	Inpatient Discharge ^c	Follow-Up Outpatient Visit	Follow-Up Call ^d
Day -28 to -2	Day -1	Day 1	Day 2-4	Day 4	Day 8 \pm 1 day	Day 14 \pm 2 days

- (a) Screening will occur at study entry. S3 subjects returning for the “Fed” repetition of the single-dose regimen will not undergo Screening assessments except as required at Day -1.
- (b) CSF collection will apply only to cohort S3 (fasted).
- (c) Discharge from the clinic may be delayed if necessary to continue monitoring for resolution of AEs.
- (d) The final follow-up assessment will occur by telephone unless abnormal, clinically significant (CS) findings were observed upon discharge. In these cases, subjects must return to the clinic for re-evaluation.

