Subjects have a known hypersensitivity to any component of the formulation of CVN766. Subjects have evidence of CS neurologic, cardiovascular, pulmonary, hepatic, hematopoietic disease, renal, metabolic, gastrointestinal, urologic, immunologic, endocrine disease, serious allergy, allergic skin rash, psychiatric disorder, or other abnormality that may impact the ability of the subject to participate or potentially confound the study results. Any finding in the subject's medical history, physical examination, or safety laboratory tests gives reasonable suspicion of a condition that might interfere with the conduct or interpretation of the study.

A complete list of exclusion criteria is provided in Section 7.2.

In addition, subjects may not use any excluded medications (including oral contraceptives as listed in Table 3), supplements, or food products. Concomitant medications and dietary products to be excluded are listed in Table 3.

Main Criteria for Evaluation and Analyses:

- Safety:

Safety parameters will include AEs, clinical laboratory results, vital signs, physical examinations, electrocardiogram (ECG). AEs will be collected from signing the informed consent form (ICF) up until dosing on Day 1 as pretreatment events (PTEs), and any event that occurs from dosing until 14 days after the last dose will be captured as an AE. Vital signs will be recorded at Screening, Inpatient Check-in (Day -1), and throughout the dosing period. Vital signs will include tympanic body temperature measurement, blood pressure, respiration rate, and pulse (beats per minute [bpm]). Triplicate orthostatic vital signs (blood pressure and heart rate) will be recorded at baseline (Check-in Day -1) 15 minutes apart. Heart rate and blood pressure will be measured after at least 5 minutes supine and again at 2 minutes after standing for all scheduled timepoints.

Standard 12-lead ECGs will be recorded at Screening, Inpatient Check-in (Day -1), and periodically throughout the dosing period. Triplicate ECGs will be taken at each timepoint.

A complete list of safety assessments is provided in Section 9.1, and the full Schedule of Study Procedures is provided in Appendix A.

- PK:

The plasma PK parameters are used as PK endpoints to determine drug exposure at each dose and facilitate dose escalations.

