6.1.1 Part 1: Single-Dose Regimen and Fasted-Fed Crossover

Approximately 40 subjects will be enrolled in 1 of the 5 single-dose cohorts (designated as S1 through S5, respectively) in an ascending fashion. Dose escalation will only occur after a fully blinded review of all available safety, tolerability, clinical laboratory results (minimally including samples collected from subjects through 72-hours post-dose), and available PK data, including at least a 72-hour follow-up of the most recent cohort.

The planned dose levels are provided in [Table 5](#). Each cohort will consist of 8 subjects randomized to CVN766 or placebo, whereby 6 subjects will receive a single dose of CVN766 and 2 subjects will receive a matching placebo under overnight fasted conditions.

Sentinel dosing (1 subject to receive CVN766 and 1 subject to receive placebo) will be used in each cohort to ensure adequate safety and tolerability evaluation prior to administering CVN766 to the remainder of subjects within the cohort. After blinded review of 24-hour post-dose safety and tolerability data, the remaining 6 subjects of each cohort may be dosed provided that the adverse event (AE) profile of CVN766 in the first 2 subjects is considered acceptable.

Subjects for all cohorts will be admitted to the study unit 1 day prior to dosing and remain in the unit for safety and PK assessments at least 72 hours after dosing. On Day 1, subjects will undergo safety monitoring (including labs, physical exam, abbreviated neuro exam, cardia telemetry at 12-hours pre-dose) and PK sampling from blood plasma through 72 hours post-dose. In addition, for cohort S3 (fasted) only, from CSF via lumbar puncture at 3 hours post-dose. For subjects participating in the SAD cohorts, the total confinement period will be 4 nights unless extended for management of AEs at the discretion of the Investigator. Follow-up assessments will occur on approximately Days 8 and 14.

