9.3.5 Follow-up Visit

The Follow-up Visit will occur by telephone approximately 14 days (± 2) after the final dose of study drug for the SAD cohorts and MAD cohorts unless abnormal CS findings were observed upon discharge or the SRG has determined additional PK sampling timepoints are indicated. In these cases, subjects must then be brought back to the clinic for re-evaluation per the investigator's discretion.

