9.8 Procedures

9.8.1 Collection and Reporting of AEs

9.8.1.1 PTE and AE Collection Period

Collection of PTEs will commence from the time the subject signs the informed consent to participate in the study and continue until the subject is first administered study medication Day 1 or until screen failure. For subjects who discontinue prior to study medication administration, PTEs will be collected for the duration of study participation.

Collection of AEs will commence from the time that the subject is first administered study medication Day 1. Routine collection of AEs will continue until 14 days following last dose.

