Concomitant medications (e)	X	X	X	X	X	X	X	X	X	X	X	X	X	X	X
Concurrent medical conditions	X	X						X							
Clinical laboratory tests (f)	X	X	X	X	X	X	X		X	X	X	X	X	X	
Hepatitis panel and HIV antibody test	X														
FSH (g)	X														
Serum Pregnancy test (hCG)	X														
Urine Pregnancy test		X						X							
CV Telemetry (n)			X	X				X	X	X					
ECG (h)	X	X	X	X	X	X	X		X	X	X	X	X	X	
PGx DNA sample collection (i)			X						X						
PGx RNA collection (j)			X						X						
PK blood collection (k)			X	X	X	X			X	X	X	X		X	
Lumbar puncture & CSF collection (k)			X												
Standardized pre-dose meal									X						

Study drug dosing			X						X						
PTE assessment (l)	X	X	X					X	X						
AE assessment (m)			X	X	X	X	X	X	X	X	X	X	X	X	X
Discharged from Clinic						X						X		X	

*S3 Cohort will return no sooner than Day 14 or 4 half-lives (whichever is greater) after Day 8 for the Fed portion. The Fed portion will commence on Day -1 will all the same schedule of events with the exception of **dosing will be post-meal.**

PGx=pharmacogenomic.

- (a) Events listed as occurring at “Inpatient Discharge” visit will occur prior to formal “Inpatient Discharge” but not necessarily at the time of Discharge.
 - (b) The Follow-up Visit will occur by telephone on Day 14 (±2) unless abnormal CS findings were observed during previous visits. In these cases, subjects must then be brought back to the clinic for re-evaluation per the investigator’s discretion.
 - (c) Vital signs (tympanic body temperature, respiration, pulse, and blood pressure) will be obtained at Screening, Inpatient Check-in (Day -1), Day 1 (pre-dose [within 1 hour and 30 minutes prior to dosing], and at 1, 2, 4-, 6-, 8-, and 12-hours post-dose), and then every 12 hours through 72 hours post-dose, and at Outpatient Visit Day 8, or Early Termination (if applicable) and as appropriate at the Follow-up Visit Day 14 (±2 days). Triplicate orthostatic vital signs (blood pressure and heart rate) will be recorded at baseline (Check-in Day-1) 15 minutes apart.
 - (d) Height and BMI will be collected at Screening only.
 - (e) Record all ongoing medications from Screening and throughout the study.

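### Cohort S3 follow-up and the return interval for the fed dose are stated inconsistently, and the Cohort 3 grid omits the Day 14 contact after the fasted dose

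*Protocol*

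**What the plan says.** The Protocol describes S3 follow-up in four places.

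- **Section 2.0, Study Summary:** "Follow-up assessments will occur on approximately Days 8 and 14 and +21 and +28 for cohort S3". No origin is given for +21 and +28. The visit table below it lists Day 8 (±1) and a Day 14 (±2) call.
- **Section 6.1.1 and Table 1:** "Follow-up assessments will occur on approximately Days 8 and 14", with no extension for S3.
- **Appendix A, Cohort 3 grid:** fasted Day 8, then no column until fed Day -1, then fed Days 1 to 4, a visit 4 days after discharge, an early-termination column and a single last contact. The note to that contact reads "The Follow-up Visit will occur by telephone on Day 14 (±2) unless abnormal CS findings were observed during previous visits".
- **Section 9.3.5:** "The Follow-up Visit will occur by telephone approximately 14 days" (±2), counted from the final dose.

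The interval before the fed period is also given twice. The Study Summary, like 6.1.1, has subjects return "no sooner than 14 days after their prior dose, or at least 4 half-lives, has lapsed based on preliminary PK data, whichever is longer". The Appendix A note says "S3 Cohort will return no sooner than Day 14 or 4 half-lives (whichever is greater) after Day 8 for the Fed portion", and the heading over the fed columns likewise counts from the Day 8 visit.

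The AE collection period does not vary. Section 9.8.1.1 says "Routine collection of AEs will continue until 14 days following last dose", and the Study Summary says "any event that occurs from dosing until 14 days after the last dose will be captured as an AE". The document holds two versions of the protocol, and the S3 follow-up sentence and the return interval are the same in both.

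**The concern.** A site cannot follow all of these statements. If +21 and +28 are meant as the contacts 7 and 14 days after the fed dose, they presuppose a gap between doses that the Study Summary sets only as a minimum and that Appendix A does not allow.

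A site that works from the Cohort 3 grid will also skip the Day 14 contact after the fasted dose, which the Study Summary and Table 1 both list. S1, S2, S4 and S5 keep that contact in their own grid.

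The first primary endpoint is the percentage of subjects with at least one treatment-emergent AE, and summaries are to separate fasted from fed. The 45 mg fasted column would then rest on a sparser schedule of AE enquiry than the other single-dose columns. S3 fasted is also the only single-dose period with a lumbar puncture.

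**Working it through.** **Inputs** (Study Summary unless noted): screening 28 days; washout at least 14 days; follow-up 14 days; stated total for the food-effect cohort about 8 weeks; windows ±1 day at Day 8 and ±2 days at Day 14; return at least 14 days after Day 8 (Appendix A). Let *g* be the number of days from the first dose to the fed dose.

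**Stated duration.** Total = 28 + *g* + 14.
- At *g* = 14: 56 days = 8.0 weeks, which reproduces the stated figure. Without the gap, 28 + 14 = 42 days = 6 weeks, which reproduces the figure for the other single-dose cohorts.

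**Earliest fed dose under Appendix A.** Day 8 + 14 = Day 22.
- If Day 22 is the fed dosing day, *g* = 21 and the total is 63 days = 9.0 weeks.
- If Day 22 is check-in with dosing on Day 23, *g* = 22 and the total is 64 days = 9.1 weeks.

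**Where +21 and +28 fall, counted from the first dose.** Days after the fed dose = 21 - *g* and 28 - *g*.

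| *g* | +21 | +28 |
|---|---|---|
| 14 | 7 | 14 |
| 15 | 6 | 13 |
| 16 | 5 | 12 |
| 18 | 3 | 10 |
| 21 | 0 | 7 |
| 22 | -1 | 6 |

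For these to serve as the 7- and 14-day contacts, 21 - *g* must lie within 7 ± 1, so *g* is 13 to 15, and 28 - *g* within 14 ± 2, so *g* is 12 to 16. Both hold for 13 to 15. With the 14-day minimum, that leaves 14 to 15.

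**Other origins.**
- Read as study Days 21 and 28 (20 and 27 days after the first dose), they fall 1 to 2 days before and 5 to 6 days after Appendix A's earliest fed dose.
- Counted from the fed dose, the total becomes 28 + 14 + 28 = 70 days = 10 weeks, and the contacts conflict with the single Day 14 call in the grid.

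**Gap after the fasted dose in the grid.** The next column after Day 8 is fed Day -1.
- At the Study Summary's minimum gap, the fed dose is on Day 15 and check-in on Day 14, about 13 days after the fasted dose.
- Under Appendix A, check-in is on Day 21 or 22, which is 20 to 21 days after the fasted dose and 13 to 14 days after the previous contact. In S1, S2, S4 and S5 the step from Day 8 to Day 14 is 6 days.

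**The case against.** The strongest reply is that the controlling text already protects follow-up. Section 9.3.5 places the last call about 14 days after the final dose. Section 9.8.1.1 and the Study Summary run AE collection to 14 days after the last dose. The Cohort 3 AE row is marked at Day 8, at fed Day -1 and in every later column. This stands, and it rules out three stronger readings.

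- A reader might infer that follow-up after the fed dose can shrink to a few days. The 6- and 7-day figures combine the Study Summary's contacts with Appendix A's interval. They become the length of follow-up only if +28 is treated as a fixed end date, which no passage says.
- A reader might infer that a subject who does not return for the fed period is never contacted after Day 8. The fasted dose is then the final dose, so Section 9.3.5 and the early-termination provisions apply. Only the grid is silent.
- A reader might infer that the schedule works only at a gap of exactly 14 days. The text says approximately, and the visit windows admit 15.

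Nor does the 8-week total show that +21 and +28 count from the first dose. The sum 28 + 14 + 14 also fits follow-up anchored on the last dose. At the Study Summary's minimum gap, fed check-in falls on Day 14 and can stand in for the missing contact.

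The Appendix A note could also be read as study Day 14, which would agree with the Study Summary. The heading over the fed columns of the same grid, which counts from the Day 8 visit, speaks against that.

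None of this reconciles the passages. The 14-day minimum is not a planned gap, and the grid's own interval moves check-in about a week past Day 14.

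**Conclusion.** The inconsistency is real and lies in text the site must carry out. S3 contacts are stated in ways that cannot all be met, and the return interval has two anchors about a week apart. At Appendix A's earliest fed dose (21 to 22 days after the first), +21 is on or one day before that dose, +28 is 6 to 7 days after it, and total duration is at least about 9 weeks against the stated 8. These positions assume that +21 and +28 count from the first dose, which the Protocol does not say. The other two origins also conflict with Appendix A.

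The definite practical loss is the Day 14 contact after the fasted dose, which leaves S3 with no scheduled contact from Day 8 to about Day 21 or 22 under Appendix A. AE collection itself is not cut, and events in that gap can still be reported at fed check-in. If the fed cohort is deferred to a higher dose level, as the Study Summary and 6.1.1 allow, the only Day 14 column in the Cohort 3 grid sits after a period that S3 does not have.

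This should be corrected, but it does not undermine the primary endpoint.

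**What to change.** Reconcile the Study Summary (follow-up sentence and total duration), Section 6.1.1 with Table 1, Section 9.3.5 and the Appendix A Cohort 3 grid with its notes. In doing so:

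- use one anchor for the return interval throughout;
- state which dose each S3 follow-up contact is counted from, in line with the Protocol's own rule of 14 days after the last dose;
- make the Cohort 3 grid agree with the Study Summary and Table 1 on the contact after the fasted dose;
- state which contacts apply if the fed period is deferred or a subject does not return;
- restate the food-effect cohort's total duration to match the interval adopted.

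Which interval is right is for the sponsor and the investigator to settle. The cost is wording in those sections, one column in the grid and at most one telephone call for each of 8 subjects.

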Additional multiple-dose cohort(s) may be added if deemed necessary by the SRG to fully characterize the safety and tolerability of CVN766. Such additional cohorts will follow the same schedule of events as for prior multiple-dose cohorts. Additional/Alternative PK timepoints may be implemented if the SRG determines this is necessary to fully characterize the PK profile of CVN766.

Subjects for all multiple-dose cohorts will be admitted to the study unit 1 day prior to dosing and remain in the unit for the duration of the dosing period and for at least 48 hours after the last dose for safety and PK assessments before discharge. On treatment Days 1 and 7, subjects will undergo safety monitoring and PK sampling from blood plasma through 48 hours post-dose and, in cohort M1 only, from urine through 24 hours post-dose. In cohorts M1 and M2, on treatment Day 7 (or last day of dosing, if extended beyond Day 7), subjects will additionally undergo PK sampling from CSF via lumbar puncture at 3 hours post-dose. If needed to resolve questions arising from prior cohorts' data, subjects in cohort M3 also may, at SRG discretion, undergo PK sampling from CSF via lumbar puncture, the choice of day (e.g., Day 1 or Day 7) and sampling time to be decided by SRG. Subjects in MAD cohorts may be asked to return to the clinic for an additional PK sample 3 days after the last dose (e.g., Day 10) depending on emerging PK data, i.e., $t_{1/2}$). The total confinement period will be 9 nights unless extended for additional dosing days or management of AEs. Follow-up assessments will occur approximately 7 and 14 days after the final dose.

A summary of the multiple-dose regimen visit schedule is presented below:

Screening	Inpatient Check-in	Dosing, PK, CSF, & Safety Assessments ^a	PK / Safety Assessments & inpatient discharge ^b	Follow-Up Outpatient Visits ^c	Follow-Up Call ^d
Day -28 to -2	Day -1	Days 1-7 ^e	1 and 2 days after last dose (e.g., Days 8-9)	3 days \pm 0 after last dose (e.g., Day 10) & 7 days \pm 1 after last dose (e.g., Day 14)	14 days \pm 2 after last dose (e.g., Day 21)

- (a) CSF sampling will occur on Day 7 in cohorts M1 and M2. Cohort M3 also may, at SRG discretion, undergo PK sampling from CSF, the choice of day and sampling time to be decided by SRG.
- (b) Discharge from the clinic is planned for Day 9 but may be delayed for additional dosing days or, if necessary, to continue monitoring for resolution of AEs.

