
Primary Objective:
 
To characterize the safety and tolerability profile of escalating dose levels of CVN766 suspension when administered as a single oral dose or daily oral doses for 7 days in healthy subjects, and to determine the recommended phase 2 dose (RP2D).
	

Secondary Objectives:
 
 To characterize the single-dose PK profile of CVN766 in plasma and CSF To characterize the multiple-dose PK profile of CVN766 in plasma and CSF To assess the effect of food on the bioavailability of CVN766 	

Exploratory Objectives:
 
 To explore possible drug metabolic enzyme and transporter polymorphisms that may contribute to variability in CVN766 PK, pharmacodynamics, or safety 	
	

Subject Population: Healthy male and female subjects 18 to 50 years old
	

Number of Subjects:
 
Each dose cohort: 8 subjects (6 active:2 placebo)
 
Estimated total: 64 subjects
 
(5 single-dose cohorts, 3 multiple-dose cohorts)
	
Number of Sites:
 
1 (Australia)

Dose Level(s):
 
Planned single-dose levels are placebo, 5 mg, 15 mg, 45 mg, 125 mg, and 250 mg CVN766.
 
Planned multiple dose levels are placebo, 45 mg, 125 mg, and 250 mg CVN766.
	
Route of Administration:
 
Oral

Duration of Treatment:
 
Single or daily oral doses for up to 7 days (+7 days as necessary to reach steady-state and as required by Safety Review Group).
	
Period of Evaluation:
 
Screening Period: up to 28 days
 
Treatment Period: 1-7 days (+7 days, as necessary).
 
Food Effect washout period (for select cohort only): at least 14 days
 
Follow-up Period: approximately 14 days
 
Total Duration:
 
 Single-dose cohorts: approximately 6 weeks Food effect cohort: approximately 8 weeks Multiple-dose cohorts: approximately 7 weeks

Main Criteria for Inclusion:
 
Healthy male and female subjects who are 18 to 55 years of age, inclusive and have a body mass index (BMI) between 18.0 and 32.0 kg/m² inclusive at Screening.
 
A complete list of inclusion criteria is provided in Section 7.1.
	

Main Criteria for Exclusion:

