9.7.3 Additional Points to Consider for PTEs and AEs

An untoward finding generally may:

- Indicate a new diagnosis or unexpected worsening of a pre-existing condition. (Intermittent events for pre-existing conditions underlying disease should not be considered PTEs or AEs)
- Necessitate therapeutic intervention
- Require an invasive diagnostic procedure
- Require discontinuation or a change in dose of study medication or a concomitant medication
- Be considered unfavorable by the investigator for any reason

- PTEs/AEs caused by a study procedure (e.g., a bruise after blood draw) should be recorded as a PTE/AE

Diagnoses vs. signs and symptoms:

- Each event should be recorded to represent a single diagnosis. Accompanying signs (including abnormal laboratory values or ECG findings) or symptoms should NOT be recorded as additional AEs. If a diagnosis is unknown, sign(s) or symptom(s) should be recorded appropriately as a PTE(s) or as an AE(s).

Laboratory values and ECG findings:

- Changes in laboratory values or ECG parameters are only considered to be PTEs or AEs if they are judged to be CS (i.e., if some action or intervention is required or if the investigator judges the change to be beyond the range of normal physiologic fluctuation). A laboratory re-test and/or continued monitoring of an abnormal value are not considered an intervention. In addition, repeated or additional noninvasive testing for verification, evaluation, or monitoring of an abnormality is not considered an intervention
- If abnormal laboratory values or ECG findings are the results of pathology for which there is an overall diagnosis (e.g., increased creatinine in renal failure), the diagnosis only should be reported appropriately as a PTE or as an AE

Pre-existing conditions:

- Pre-existing conditions (present at the time of signing of the ICF) are considered concurrent medical conditions and should NOT be recorded as PTEs or AEs. Baseline evaluations (e.g., laboratory tests, ECG, X-rays, etc.) should NOT be recorded as PTEs unless related to study procedures.
- If a subject has a pre-existing episodic condition (e.g., asthma, epilepsy), any occurrence of an episode should only be captured as a PTE/AE if the episodes become more frequent, serious, or severe in nature; that is, investigators should ensure that the AE term recorded captures the change in the condition from Baseline (e.g., “worsening of...”)

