9.7.7 Relationship to Study Procedures

Relationship (causality) to study procedures should be determined for all PTEs and AEs.

The relationship should be assessed as Related if the investigator considers that there is a reasonable possibility that an event is due to a study procedure. Otherwise, the relationship should be assessed as Not Related.

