12.1.4 Safety Analysis

12.1.4.1 AEs

All AEs will be coded by system organ class (SOC) and preferred term (PT) using MedDRA. Treatment-emergent AEs with onset occurring within 30 days (onset date – last date of dose +1 \leq 30) after study drug administration will be listed and included in the summary tables. Treatment-emergent AEs will be summarized by pooled placebo, each CVN766 dose level and CVN766 overall by SOC and PT. The following summary tables will be included in the report: summary of TEAEs and drug-related AEs, relationship of AEs to study drug (related vs. not-related), severity of AEs, and related AEs. AEs leading to study drug discontinuation and SAEs will be listed. Data listings will be provided for all AEs, including PTE, TEAEs, AEs leading to study drug discontinuation, and SAEs. All AEs will be listed.

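### Lumbar puncture is tied to dose cohort and its adverse events count in the primary TEAE percentage, so the by-dose summary against pooled placebo can show spurious differences

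*Protocol*

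**What the plan says.** **Who is punctured.** In the single-dose part, CSF is taken "for cohort S3 (fasted) only, from CSF via lumbar puncture at 3 hours post-dose". In the multiple-dose part, "CSF sampling will occur on Day 7 in cohorts M1 and M2"; M3 may be added if the SRG decides so, on a day and at a time the SRG chooses (Section 6.1.2). S1, S2, S4, S5 and the S3 fed period have no puncture. Section 9.1.1.1 makes CSF collection mandatory in the cohorts concerned and states no exemption for placebo subjects.

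**What counts as an event.** Section 9.7.3: "PTEs/AEs caused by a study procedure (e.g., a bruise after blood draw) should be recorded as a PTE/AE". The first primary endpoint in Section 5.2.1 is the percentage of subjects with at least one TEAE, and procedure-related events are not excluded. The planned punctures follow dosing, so events they cause start after dosing.

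**What is recorded about cause.** Section 9.7.7: "Relationship (causality) to study procedures should be determined for all PTEs and AEs". Section 9.8.1.2 adds that details of the suspected procedure are documented.

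**How events are tabulated.** Section 12.1.4.1: "Treatment-emergent AEs will be summarized by pooled placebo, each CVN766 dose level and CVN766 overall by SOC and PT". The causality tables named there concern study drug only. On grouping, the Study Summary says "Placebo data will be pooled across single-dose cohorts and separately pooled across multiple-dose cohorts"; it also keeps fasted and fed apart and gives separate single-dose and multiple-dose totals for CVN766. Section 12.1.4 repeats none of this and names one pooled placebo and one CVN766 overall.

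**The concern.** Puncture was assigned by cohort, and cohort is dose. Any event the needle causes is therefore confounded with dose in the primary endpoint, and the pooled comparator does not correct for it because its punctured share differs from that of every active cohort as planned. Randomised placebo within each cohort would balance the procedure; pooling across cohorts undoes that balance.

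The drug-relatedness tables are a weak filter. Section 9.7.6 classes an event as related if drug involvement can be argued, even where other factors may be responsible. Section 4.1 lists mild headache among the commonest events with other selective Ox1R antagonists, so a headache after a puncture done 3 hours post-dose could be attributed to CVN766. The protocol gives no puncture event rate, but it does schedule puncture-site assessments for S3 fasted.

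At stake is the reading of tolerability by dose. The Study Summary's primary objective includes choosing a recommended phase 2 dose.

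**Working it through.** **Inputs from the protocol.** Eight subjects per cohort, 6 active and 2 placebo; five single-dose and three multiple-dose cohorts. Check: 8 × (5 + 3) = 64, which agrees with "Estimated total: 64 subjects". Pooled placebo is 5 × 2 = 10 single-dose and 3 × 2 = 6 multiple-dose, counting each subject once.

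**Punctured share as planned.**

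| Group | Punctured |
|---|---|
| S3 fasted, active | 6/6 |
| S1, S2, S4, S5, active | 0/6 each |
| Single-dose placebo | 2/10 |
| M1 and M2, active | 6/6 each |
| M3, active | 0/6 (optional) |
| Multiple-dose placebo | 4/6 |

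If Section 12.1.4 were applied literally, without the Study Summary's split, the shares by dose level would be 0 at 5 and 15 mg, 12/12 at 45 mg (S3 and M1), 6/12 at 125 mg (S4 and M2), 0/12 at 250 mg (S5 and M3), and 6/16 in one placebo column.

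**Assumptions, not in the documents.** The drug is inert; background TEAE risk b = 30%; a puncture adds an event with probability q = 10 to 40%, independently of background.

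**Formulas.**
- Punctured cohort: p = 1 - (1 - b)(1 - q)
- Single-dose placebo: (8b + 2p)/10
- Multiple-dose placebo: (2b + 4p)/6

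**Results at b = 30%** (risks in %, differences from placebo in percentage points).

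| q | Punctured cohort | Single-dose placebo | S3 minus placebo | Other single doses minus placebo | Multiple-dose placebo | M1, M2 minus placebo | M3 minus placebo |
|---|---|---|---|---|---|---|---|
| 10% | 37.0 | 31.4 | +5.6 | -1.4 | 34.7 | +2.3 | -4.7 |
| 20% | 44.0 | 32.8 | +11.2 | -2.8 | 39.3 | +4.7 | -9.3 |
| 30% | 51.0 | 34.2 | +16.8 | -4.2 | 44.0 | +7.0 | -14.0 |
| 40% | 58.0 | 35.6 | +22.4 | -5.6 | 48.7 | +9.3 | -18.7 |

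With b ranging over 10 to 30%, the ranges widen to +6 to +29 for S3, -1 to -7 for the other single doses, +2 to +12 for M1 and M2, and -5 to -24 for M3.

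**In subjects.** One of six is 16.7 points. At b = 30%, the S3 artefact is 5.6/16.7 to 22.4/16.7, about 0.3 to 1.3 subjects; the M3 artefact is 4.7/16.7 to 18.7/16.7, about 0.3 to 1.1 subjects.

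**Against sampling noise.** By exact binomial calculation at b = 30%, a punctured active cohort of six shows more TEAE subjects than an unpunctured one with probability 48% (q = 10%) to 77% (q = 40%). The reverse has probability 28% to 10%.

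**If M3 is punctured on the same day as M1 and M2,** every multiple-dose group is fully punctured and the differences there are zero. S3 against single-dose placebo is unaffected.

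**Would puncture-matched placebo be better?** Root-mean-square error of the placebo percentage (bias and sampling error together), b = 30%, q = 10 to 40%, in points:

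| Cohort | Pooled placebo | Matched placebo |
|---|---|---|
| S3 | 16-27 (n = 10) | 34-35 (n = 2) |
| M1, M2 | 20-22 (n = 6) | 24-25 (n = 4) |
| M3 | 20-27 (n = 6) | 32 (n = 2) |

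For example, S3 at q = 40%: pooled variance is (8 × 0.21 + 2 × 0.2436)/100 = 0.0217 and squared bias is 0.224² = 0.0502, so the error is √0.0719 = 26.8 points; matched, √(0.2436/2) = 34.9 points. Pooling has the smaller total error throughout.

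**The case against.** The best counter-argument is that this belongs to the SAP. Section 12.1 leaves variable definitions and methodology to it, nothing forbids a table excluding procedure events, and the data for one must be collected. The SOC/PT tables and full listings also let a reader see which events drive a cohort's percentage. This stands to the extent that nobody can say the final report will mislead. It does not dispose of the point: the protocol itself fixes the pooling and names causality tables for study drug only, and Section 12.1.4 states the grouping more loosely than the Study Summary does.

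A reader might infer that the tables will show a mid-dose effect and flatter the top dose. The documents do not support that. M3 may be punctured. Mid-dose describes S3 only; in the multiple-dose part the raised cohorts are the lowest and middle doses. At 250 mg single dose the deficit is only about 1 to 7 points and is shared by every unpunctured single dose.

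Nor is a formal comparison biased: no test of TEAEs is planned. Escalation rests on SRG review of blinded data (Section 6.1.3), not on this table. The S3 fasted and fed AE percentages differ in the same way, but the food objective is bioavailability, so that is a secondary matter. The shorter wording in Section 12.1.4 is incomplete beside the Study Summary rather than clearly opposed to it.

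**Conclusion.** The concern holds as a limited, correctable weakness in a descriptive primary summary. Puncture is tied to cohort, its events enter the any-TEAE percentage, and pooled placebo has a different punctured share from each active cohort as planned. The by-dose table can therefore show an excess without any drug effect, chiefly in S3, and a deficit at 250 mg multiple dose if M3 is not punctured. At the assumed rates the size is about +6 to +22 points for S3 and -5 to -19 for M3, which is at most a little over one subject in six. The direction follows from the design as long as punctures cause any events; the size rests entirely on the assumed rates and on placebo subjects in the punctured cohorts being punctured too.

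A reader might also conclude that pooled placebo is the wrong comparator and should be replaced by placebo matched on puncture. The error calculation does not support this: with 2 to 4 matched subjects, the lost precision costs more than the removed bias.

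**What to change.** In Section 12.1.4.1:

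1. Keep the all-TEAE table by dose with pooled placebo.
2. Add the same table excluding TEAEs that the investigator relates to lumbar puncture, using the procedure relationship and procedure details already documented for each event. A subject with another TEAE still counts.
3. Mark the columns in which puncture was done, and settle the M3 column by what actually happened.
4. Show placebo by puncture status only as a descriptive supplement, not as the comparator.

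Throughout Section 12.1.4, carry over the Study Summary's grouping: single-dose and multiple-dose placebo separate, CVN766 totals separate, fasted and fed separate.

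The cost is a few extra tables and no new data. The second table depends on the investigator's attribution, which is blinded to treatment but not to whether a puncture took place, so a drug event could be assigned to the needle. That is why both tables are needed.
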